#### 4.5.5 Vital signs

- SBP, DBP
- Heart rate

The measurements at each visit during the titration phase will be summarized for each time point descriptively by parameter including absolute changes from baseline. Arithmetic mean plots including standard deviation over time will be presented.

Frequencies of participants with a decrease in SBP from the previous visit by >30 mmHg will be presented. In addition, frequencies for the following combinations of the above criteria will be summarized reflecting the up-titration criteria:

- $\geq$ 105 mmHg SBP *and*  $\leq$ 30 mmHg decrease from previous visit (dose increase),
- ≥105 mmHg SBP *and* >30 mmHg decrease from previous visit *or*

<105 mmHg and  $\geq$ 90 mmHg SBP (dose maintenance),

• <90 mmHg SBP (dose decrease to previous level).

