1.3 Schedule of activities (SoA)

Table 1-2 Schedule of activities: Part 1 – Screening (Visit 1) and titration phase (Visits 2 to 6)

					Ti	itrati	on				
	Visit number	1		2		3,	4,	5		6	
	Study week	-1		1		2,	3,	4		5	
	Study day	-2		1		8,	15,	22		29	
	Permissible time window (days)	-28 to -2		n/a			±1			±2	
	Time (hours relative to dose)		pre	1-2	2-4	pre	1-2 ²	2-4	pre	1-2 ²	2-4
	Written informed consent	•									
	Allocation of screening number	•									
study Initiation	Demographic data	•									
atio	Medical/surgical history (general and cardiological)	•									;)
nitie	Previous medication (medication history)	•									
=	History on use of caffeine, alcohol, tobacco	•									
	Check of in-/exclusion criteria	•	•								
	Determination of study eye		•								
	Randomization		•								
itio	Dose titration decision					•					
tud	Administration of study intervention (time 0)			•			•			•	
S	Collection of unused study intervention					•			•		
·=	Dispensation of study intervention				•			•			•
	Recording of AEs, concomitant medication		\rightarrow								
_	Physical examination, height, weight	•									
ety.	Checking fasting / feeding state	•	•			•			•		
Safety⁴	Blood pressure, pulse rate ¹	•	•	•²	•	•	•²	•	•	•²	•
-,	12-lead ECG (triplicate) 1	•	•	•²	•	•	● ²	•	•	● ²	•
	Urine pregnancy test (women)		•			•			•		
	Hematology, biochemistry	•	•			•			•		
4,5	Hormones	•					$\begin{array}{cccccccccccccccccccccccccccccccccccc$				
pod ling	Biomarker (plasma, serum)		•			•					•
Blood sampling ^{3,4}	Pharmacogenetics (optional)		•								
Sa	Serum pregnancy test (women)	•	•			•			•		
	Pharmacokinetics		•	•²	•	•	•²	•	•	•2	•
	Visual acuity test (BCVA)	•	•								
S ₄ S	Tonometry	•	•			•			•		
riol ral)	Structural OCT	•	•			•			•		•
Ophthalmolog examinations (bilateral)	Anterior and posterior segment examination	•									
htth am (bil	OCT angiography	•	•		•	•		•	•		•
őě	7-field color fundus photography (DRSS)	•									
	Fluorescein angiography (DRSS)	•									

AE = adverse event; BCVA = best corrected visual acuity; DRSS = used for assessment of diabetic retinopathy severity score; ECG = electrocardiogram; OCT = optical coherence tomography

¹ Blood pressure, pulse rate and ECG always to be measured in supine or semi-supine position after ≥ 5 minutes rest and before any blood draws

² Minimum interval of 1 hour to prior and subsequent examinations

³ Blood sampling to be performed before fluorescein angiography, to avoid interferences with analytics

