- 4 To be done pre-dose before study intervention administration, except for Visit 7 taking place in the afternoon

09 FEB 2023 Page: 16 of 95

Table 1-4	Schedule of activities:	Parts 1 and 2 - Visits 7 to 16
I UDIC I-T	Ochicadic of activities.	i di to i di la L - Violto i to i o

	Visit number	7 ¹	8	9	10	11	12	13	14	15 EoT	16 EoS
	Study week	7	9	13	17	21	25	33	41	49	53
	Study day	43	57	85	113	141	169	225	281	337	365
	Permissible time window (days)	±2	±2	±7	±7	±7	±7	±7	±7	±7	±7
~> >	Dispensation of study intervention	•	•	•	•	•	•	•	•		
Study interv.	Administer study intervention (after blood draws)		•	•	•	•	•	•	•		
S.E	Collection of unused study intervention	•	•	•	•	•	•	•	•	•	
	Record AEs and concomitant medication	\rightarrow									
4	Physical examination, weight									•	
Safety ⁴	Blood pressure, pulse rate ²	•	•	•	•	•	•	•	•	•	•
Sa	12-lead ECG ²	•	•		•		•	•	•	•	
	Dispensation of urine pregnancy test ³						•	•	•		
Blood sampling ^{4,5}	Hematology, biochemistry	•	•	•	•	•	•	•	•	•	•
od jing	Biomarker samples: plasma, serum	•	•	•	•	•	•			•	
Blo mp	Serum pregnancy test (women)	•	•	•	•	•	•	•	•	•	•
Sa	Pharmacokinetics	•	•	•	•	•	•				
	Visual acuity test (BCVA)		•		•		•	•	•	•	•
\mathcal{Q}_{4}^{S}	Tonometry	•	•	•	•	•	•	•	•	•	•
a jog	Structural OCT	•	•	•	•	•	•	•	•	•	•
Ophthalmolog examinations ⁴ (bilateral)	Anterior and posterior segment examination			•			•			•	
tt (bili	OCT angiography (optional in Part 2)	•	•	•	•	•	•	•	•	•	•
ŏä	7-field color fundus photography (DRSS)			•			•			•	
	Fluorescein angiography (DRSS)						•			•	

AE = adverse event; BCVA = best corrected visual acuity; DRSS = used for assessment of diabetic retinopathy severity score; ECG = electrocardiogram; EoS = End of study; EoT = end of treatment; OCT = optical coherence tomography

- 1 Visit 7 should take place in the afternoon, PK and biomarker samples to be taken at 4 to 8 hours after dosing
- 2 Blood pressure, pulse rate and ECG always to be measured in supine or semi-supine position after ≥ 5 minutes rest and before any blood draws
- 3 Additional urine pregnancy test to be provided to women for use off-site 4 weeks after the respective visit
- 4 To be done pre-dose before study intervention administration, except for Visit 7 taking place in the afternoon
- 5 Blood sampling to be performed before fluorescein angiography to avoid interferences with analytics

2. Introduction

As of amendment 3, this Section and its sub-sections were integrated from Master Protocol.

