Runcaciguat (BAY 1101042) is a representative from a new class of drugs, the soluble guanylate cyclase (sGC) activators. The sponsor is developing sGC activators for the treatment of microangiopathies, namely chronic kidney disease (CKD) and non-proliferative diabetic retinopathy (NPDR). For both indications, proof-of-concept studies are currently ongoing, one being the NEON-NPDR study.

For the NPDR indication, the treatment is intended to

- Prevent progression of diabetic retinopathy and vision-threatening complications
- Reverse retinal changes attributed to diabetic retinopathy
- Maintain visual acuity.

09 FEB 2023 Page: 17 of 95

Runcaciguat will be investigated in a formulation of modified-release (MR) tablets, which result in peak plasma concentrations at approximately 10 hours post dose and a peak-to-trough concentration ratio of 2:1. The terminal half-life of runcaciguat in plasma ranged from approximately 14 to 21 hours in healthy study participants.

Runcaciguat, given as MR tablets, showed vasodilatory effects at doses from 20 mg to 90 mg once daily without clinically relevant signs of hemodynamic intolerance. Once-daily doses up to the highest investigated dose of 90 mg administered over 7 days were safe and well tolerated by healthy participants.

Other indications under development for runcaciguat include chronic kidney disease. A clinical study in patients with chronic kidney disease (CONCORD study 18748; EudraCT: 2019-003297-53) started in 2020 and is ongoing in parallel. In that study, patients are treated with once-daily doses of runcaciguat titrated up to 120 mg. The current recruitment status is summarized in Section 2.3.1.

Further information on pre-clinical and available clinical data relevant in the context of this study are provided and discussed in Section 2.3. Additional information is given in the most recent version of the IB.

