Repeat or unscheduled samples may be taken for safety reasons or for technical issues with the samples.

After signing an informed consent, participants will be invited to a screening visit, Visit 1, to evaluate their eligibility for this study. Eligible patients with NPDR who meet all of the inclusion criteria and none of the exclusion criteria, will be randomized to treatment with either runcaciguat or placebo. During the treatment period, participants will be monitored for adverse events and concomitant medication, and undergo the assessments outlined in the SoA, Section 1.3.

The treatment period comprises Visits 2 to 15 (Week 1 to Week 49), the End-of-Treatment visit.

An End-of-Study visit, Visit 16, is planned approximately 28 days after last administration of study drug.

- The maximum amount of blood collected from each participant over the duration of the study, including any extra assessments that may be required, will not exceed 300 mL.
- Repeat or unscheduled samples may be taken for safety reasons or for technical issues with the samples.

09 FEB 2023 Page: 48 of 95

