9.4.5 Other safety analysis

All safety analyses will be made on the Safety Population. A detailed description will be given in the statistical analysis plan.

For the secondary objective (safety) of the study, the following additional endpoints will be considered and analyzed:

- Laboratory parameters
- Vital signs
- Electrocardiography

Quantitative data will be described by the following summary statistics: arithmetic mean, standard deviation, median, minimum and maximum. These summary statistics will be presented by treatment for the original data as well as for the difference to baseline. Frequency tables will be provided for qualitative data. Laboratory data outside the reference

09 FEB 2023 Page: 64 of 95

range will be listed and flagged with 'L' for low and 'H' for high. Additional tables with all abnormal values will be presented.

Graphical displays of individual data as well as mean values with standard deviation will be included.

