#### 4.1.2 End of Treatment

Beside the Visit 15 EoT, the EoT values will also be derived to account for eCRF entry errors. The EoT value is the value of the visit at the last treatment day. In case no visit occurred at the last treatment day, the EoT value is the value of the first visit after last treatment.

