#### 4.1.4 Discontinuations

Participants who discontinue the study prematurely (i.e., dropout) will not be replaced. A temporary discontinuation exceeding 14 consecutive days or 21 days overall results in a permanent discontinuation. If unexpectedly high dropout rates occur (e.g., due to COVID-19), the number of randomized participants may be increased by up to 20%. For further details with respect to the analysis of dropouts refer to the Section 4.1.3 on handling of Missing Data.

A participant may withdraw from the study at any time at his/her own request or may be withdrawn at any time at the discretion of the investigator for safety, behavioral, or compliance reasons. This includes cases where, in the investigator's opinion, continued participation in the study would be harmful to the participant's well-being. This is expected to be uncommon. At the time of discontinuing from the study, if possible (if the participant is not lost to follow-up and if the health status of the participant allows), Visit 15 should be conducted as early discontinuation visit, followed by safety follow-up (Visit 16). Data collected at early discontinuation visits will be handled as follows: If a valid DRSS assessment is available from the early discontinuation visit, this value will be considered for analyses for the respective visit. Other variables assessed at early discontinuation visits will be listed for individual follow-up but not be considered for summary statistics.

Participants who permanently discontinue study treatment are invited to continue to attend all protocol-specified study visits. Values assessed at visits after discontinuation from study treatment will be listed for individual follow-up but not be considered for summary statistics. All values assessed after study treatment discontinuation will be flagged in the listings.

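### SAP 4.5.5 limits the by-visit table of blood pressure and heart rate to the titration phase, so measured blood pressure is not tabulated for 9 of 14 on-treatment visits

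*SAP*

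**What the plan says.** SAP 4.5.5 covers systolic and diastolic pressure and heart rate. Its scope sentence is: "The measurements at each visit during the titration phase will be summarized for each time point descriptively by parameter including absolute changes from baseline". The headings of Protocol Tables 1-2 and 1-3 fix which visits that means: "Screening (Visit 1) and titration phase (Visits 2 to 6". Protocol Section 8 sets the whole period: "The treatment period comprises Visits 2 to 15 (Week 1 to Week 49), the End-of-Treatment visit".

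Other passages are wider:

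- Protocol Table 1-4 schedules blood pressure and pulse at every visit from 7 to 16. A footnote sets Visit 7 apart: "Visit 7 should take place in the afternoon, PK and biomarker samples to be taken at 4 to 8 hours after dosing".
- Protocol 9.4.5 lists vital signs among the safety endpoints and says: "These summary statistics will be presented by treatment for the original data as well as for the difference to baseline". It names no phase.
- SAP 4.1.1 provides by-visit statistics with change from baseline where they apply. For runcaciguat it adds a by-visit breakdown by the maintenance dose, defined as the level reached at Visit 6.
- SAP 4.8 lists one departure from the protocol, the removal of serum lipoprotein.

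Two rules bear on participants who stop early. SAP 4.1.4 says of non-DRSS data: "Other variables assessed at early discontinuation visits will be listed for individual follow-up but not be considered for summary statistics". SAP 4.1.2 derives an end-of-treatment value: "In case no visit occurred at the last treatment day, the EoT value is the value of the first visit after last treatment".

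**The concern.** The specific section is narrower than the general section and the protocol, and the narrowing is not declared. A programmer would normally follow the specific section. Laboratory values (4.5.3), eGFR (4.5.4) and ECG (4.5.6) carry no phase limit, so the limit on vital signs reads as intended.

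Hypotension with compensatory tachycardia is the first risk in Protocol Table 2-2. The chronic kidney disease study cited for tolerability treated for 8 weeks (Protocol 2.3.1), while this trial treats for 48. A table that ends at Day 29 cannot show blood pressure during maintenance. It also cannot deliver the by-visit breakdown by maintenance dose beyond Visit 6, the visit at which that dose is defined.

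**Working it through.** **1. The plan's own duration.** Weeks on treatment = (study day − 1)/7. Visit 15 is Day 337, so (337 − 1)/7 = 48.0 weeks, which reproduces the stated duration.

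**2. Share covered by the table.** Visit 6 is Day 29, so (29 − 1)/7 = 4.0 weeks. 4/48 = 8.3% is covered and 48 − 4 = 44 weeks (91.7%) is not.

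**3. Visits.** On treatment, Visits 2 to 15 make 14. Titration, Visits 2 to 6, makes 5. That leaves 14 − 5 = 9 (Visits 7 to 15). With follow-up Visit 16, 10 visits with scheduled blood pressure fall outside the table.

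**4. Timing against the peak.** Protocol Section 2 says of the modified-release tablets: "which result in peak plasma concentrations at approximately 10 hours post dose and a peak-to-trough concentration ratio of 2:1".

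| Reading | Hours after dose | Distance from the peak at about 10 h |
|---|---|---|
| Part 1, Visits 2 to 6, first window | 1–2 | 8–9 h before |
| Part 1, Visits 2 to 6, second window | 2–4 | 6–8 h before |
| Visit 7, if taken close to the blood samples | 4–8 | 2–6 h before |
| Pre-dose trough | about 24 | about 14 h after |

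In Part 2 the safety measurements up to Visit 6 are pre-dose (footnote to Table 1-3). Visits 8 to 15 are pre-dose in both parts (footnote to Table 1-4). Visit 7 is therefore the only scheduled on-treatment visit with a post-dose blood pressure in Part 2, and the one likely to lie nearest the peak in either part.

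**5. Readings on the target dose.** The step to 120 mg comes at Visit 5 (Protocol 1.1). Part 2 readings are pre-dose, so its Visit 5 reading precedes that step. For the 40 of 52 planned runcaciguat participants who are in Part 2, the table holds at most one reading on 120 mg, the Visit 6 trough. SAP 4.5.2 assigns week 5 onward to maintenance at 120 mg, and Visit 6 is in week 5. On that definition even this reading could fall outside titration.

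**6. What other outputs cover after titration.**

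| Output | After Visit 6? | Measured blood pressure? |
|---|---|---|
| 4.5.5 descriptive table | No | Yes |
| 4.5.5 mean plots; systolic drop and category frequencies | No visit limit written | Yes |
| 4.5.2 adverse events by dose level and phase | Yes | No |
| 4.5.6 heart rate from ECG (scheduled at Visits 7, 8, 10, 12–15) | Yes | No |

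**The case against.** The strongest reply is that the sentence adds detail and is not meant to set a limit. It speaks of time points, and several time points within a visit exist only at Visits 2 to 6 in Part 1. The plots over time and the systolic frequencies in the same section carry no phase limit, SAP 4.1.1 supplies by-visit statistics, and the table specifications are a separate document. This is a fair reading, and it may be what the authors meant. But the sentence is not confined to Part 1, the general rule applies only where applicable, and the category frequencies are tied to the up-titration criteria, so their scope after titration is unclear too. The ambiguity stands.

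A reader might infer more than the documents support:

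- **That hypotension goes unsummarised for 44 weeks.** It does not. SAP 4.5.2 tabulates treatment-emergent events by dose level for titration and maintenance. It does the same for events of special interest, which include syncope. However, a low reading becomes an adverse event only if the investigator judges it clinically significant (Protocol 10.3.1), so these tables complement measured values and do not replace them.
- **That each omission flatters the drug.** Protocol 4.3 reports first-day changes 2.5 times (diastolic pressure) and 3.5 times (heart rate) those on repeated dosing, and Protocol 2.3.1 also describes larger effects after the first dose. Visits 8 to 15 add trough readings. A discontinuation-visit value may be off drug, given a half-life of about 14 to 21 hours.
- **That discontinuation-visit values are lost.** They are listed, and keeping them out of by-visit means is defensible. What is missing is how this rule fits with the derived end-of-treatment value.
- **That Visit 7 gives blood pressure at 4 to 8 hours.** That window is written for PK and biomarker samples. For blood pressure the table gives only the afternoon visit and the order before blood draws.

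**Conclusion.** The point holds as a conflict of scope. SAP 4.5.5 as written omits Visits 7 to 16 from the descriptive table of systolic pressure, diastolic pressure and vital-sign heart rate. That is 9 of 14 on-treatment visits and 44 of 48 weeks. It disagrees with Protocol 9.4.5 and SAP 4.1.1, and SAP 4.8 does not declare it. The gap that no other output clearly fills is a by-visit table of measured blood pressure in maintenance, including Visit 7. The direction of any distortion cannot be stated.

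This rests on two assumptions: that titration means Visits 2 to 6, as in the schedule headings, and that the unseen table specifications follow 4.5.5. If they already cover all visits, only the SAP wording needs correction. The proof-of-concept decision is unaffected. The change should still be made, because it concerns the first listed risk and uses data already collected.

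**What to change.** - **SAP 4.5.5, scope.** Replace the words that confine the summary to titration visits with: at each scheduled visit (Visits 2 to 16), and at each time point within Visits 2 to 6 in Part 1.
- **Visit 7.** Show it as its own row, identified as post-dose (afternoon), and do not pool it with trough visits. Do not label the blood pressure row with an hour window unless the actual times support it.
- **Systolic frequencies.** State which visits are covered by the counts of drops above 30 mmHg and by the category counts. A new table of worst values per participant is not needed. The categories combine a level with a change since the previous visit, so it would require a new ordering rule.
- **SAP 4.1.2 and 4.1.4.** Add a cross-reference saying whether the derived end-of-treatment vital-sign value of early stoppers enters an end-of-treatment summary row.
- **SAP 4.8.** If the titration-only scope is intended, declare it there with a reason.

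The cost is a few lines of SAP text and a few table rows. No new data are needed.

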## 4.5.6 Additional Safety Assessments

## ECG

During Part 1 up to study Visit 6 (inclusive), triplicate ECG tracings will be recorded. These triplicate tracings may be transferred to a central ECG reading center for later QT evaluation. The results of the QT evaluations may be reported separately. For part 2, single ECGs will be recorded and transferred to a central ECG reading center for evaluation.

ECG parameters (ventricular rate, PR interval, QRS-duration, and QT interval) will be determined and transferred to the database. The QT interval will also be corrected for the heart rate using Fridericia's method (QTcF), i.e., by dividing the observed QT interval by the cube-root of RR:

$$QTcF = \frac{QT}{\sqrt[3]{RR}}$$

Corrected QT intervals and the heart rate will be provided by the central ECG lab and summarized descriptively by parameter including absolute changes from baseline.

A frequency table will be provided for the ECG findings, presence of sinus rhythm and atrial fibrillation and overall interpretation of ECGs (normal; abnormal, clinically insignificant; abnormal, clinically significant), by visit including any visit.

## 4.6 Other Analyses

## 4.6.1 Pharmacokinetics

All analyses of PK will be made on the PK analysis set.

The concentration data will be included in a Pop-PK model, and this will be described in a separate M&S Analysis Plan. The results will be reported in a separate M&S Report separately from the main clinical study report.

The concentration-time courses of runcaciguat will be tabulated separated by dose group and sampling time window. The following statistics will be calculated for each of the sampling windows: geometric mean, geometric SD (re-transformed SD of the logarithms) and CV, arithmetic mean, SD and CV, minimum, median, maximum values, and the number of measurements. These statistics (except for minimum and maximum) at any time will only be calculated if at least 2/3 of the individual data were measured and were above the LLOQ. For their calculation, a data point below LLOQ will be substituted by one half of this limit. Statistics will be marked in the tables if values below the LLOQ are included in their calculation.

Furthermore, the following parameters will be analyzed by the statistics mentioned above:

- Ctrough
- C1-2 hours
- C2-4 hours

## 4.6.2 PK/PD by groups and by dose level maintained at least for 50% of the study

- CRT by Ctrough
- Retina perfusion by Ctrough

Scatter plots for change from baseline of CRT vs. Ctrough and changes from baseline of retina perfusion vs. Ctrough will be provided by dose level maintained at least for 50% of the study.

#### 4.6.3 Biomarkers

All Biomarker analyses will be performed on the PPS. Biomarker analyses include the following endpoints:

- HbA1c
- Plasma cyclic guanosine monophosphate (cGMP)
- plasma kynurenine
- serum cystatin C (CysC)
- plasma norepinephrine (NE) (optional if measured)

#### **Descriptive Statistics**

Summary statistics including ratio to baseline and change to baseline will be presented (using arithmetic and geometric means) and frequency tables for qualitative data will be provided.

All biomarkers are assumed to be log-normally distributed and will be summarized using number of participants, geometric mean, geometric SD, arithmetic mean, arithmetic SD, minimum, median, IQR, maximum. In addition, ratios to baseline with 95% CI will be provided. These summary statistics will be presented at each planned time point by study intervention for the observed data.

In addition, geometric mean plots of biomarker absolute concentrations, geometric mean plots (including one standard deviation range) of biomarker ratio to baseline and arithmetic mean plots (including one arithmetic standard deviation range) of biomarker change to baseline over time will be presented for all biomarkers. Individual plots of biomarker concentrations will be presented for the absolute concentrations, the ratio to baseline, and change to baseline.

